[figure not shown]

Evaluation of Metabolomic Biomarkers in Pulmonary Fibrosis

Study Protocol and Statistical Plan

We designed a single-center, prospective, cross-sectional investigation involving patients diagnosed with Pulmonary Fibrosis. Participants are recruited from the Interstitial Lung and Rare Diseases Outpatient Clinic at the Vanvitelli Respiratory Diseases Clinic, Monaldi Hospital, Naples, Italy. Patients were included if they met the following criteria: 1) Confirmed IPF diagnosis based on the 2018 ATS/ERS/JRS/ALAT guidelines [PMID: 30168753] within the past five years 2) diagnosis of other fibrotic interstitial lung disease different from IPF 3) age \geq 40 years, 4) ability to provide informed consent. Exclusion criteria included: 1) a current diagnosis of asthma or chronic obstructive pulmonary disease (COPD), 2) an acute Pulmonary Fibrosis exacerbation within the past three months. Demographic and anthropometric data—including sex, smoking history, and comorbidities—are systematically recorded. All participants undergo pulmonary function testing, including spirometry, body plethysmography, and single-breath diffusing capacity of the lungs for carbon monoxide (DLCO), following the 2022 ATS/ERS guidelines [PMID: 34949706]. Tests are performed using the Vynntus BODY system (Vyaire Medical), and the following parameters were measured: FEV₁, FEV₁%, FVC, FVC%, FEV₁/FVC, TLC, TLC%, RV, RV%, DLCO, and DLCO% [PMID: 22743675, PMID: 28893868]. Additionally, arterial blood gas (ABG) analysis was conducted to assess pH, partial pressure of oxygen (pO₂), partial pressure of carbon dioxide (pCO₂), bicarbonate (HCO₃⁻), and lactate levels. Functional capacity is evaluated using the 6-minute walk test (6MWT), performed according to ATS guidelines [PMID: 12091180]. The Gender-Age-Physiology (GAP) index was calculated to stratify IPF patients into three risk stages based on clinical (sex, age) and physiological (FVC, DLCO) parameters, providing an estimate of 1-, 2-, and 3-year mortality [PMID: 22586007]. To enhance prognostic accuracy, the Distance-Oxygen-Gender-Age-Physiology (DO-GAP) index was also determined by incorporating 6MWT distance and exertional hypoxemia [PMID: 37228268].

Study Protocol Design

Statistical plan

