Baseline population characteristics, comparing the control group and Pulmonary Fibrosis patients. In particular, the χ^2 test or Spearman's rank correlation (Rho) was applied to categorical variables according to their distribution, while the Wilcoxon-Mann-Whitney test was used for continuous variables to identify significant differences between the two groups (controls and PF). For univariate correlations, Pearson's or Spearman coefficient are used as appropriate. These statistical methods provide a comprehensive understanding of the clinical and biochemical differences between the two groups and the relationships among the fatty acids studied. Finally, we evaluated the diagnostic potential of significant FAs for IPF using Receiver Operating Characteristic (ROC) curves. A p -value < 0.05 was considered statistically significant.

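### The ROC step seeks diagnostic potential for IPF, but the only stated contrast is controls versus pooled pulmonary fibrosis and the ROC non-cases are not named

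*Combined protocol and SAP*

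**What the plan says.** The opening paragraph of the Study Protocol and Statistical Plan describes a "cross-sectional investigation involving patients diagnosed with Pulmonary Fibrosis". Its inclusion criteria list two kinds of patient under that label: "Confirmed IPF diagnosis based on the 2018 ATS/ERS/JRS/ALAT guidelines" and "diagnosis of other fibrotic interstitial lung disease different from IPF". No patient can meet both, so they must be alternatives, and the PF group contains both strata.

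The section headed Statistical plan opens with "Baseline population characteristics, comparing the control group and Pulmonary Fibrosis patients". It then gives the between-group tests, whose purpose is "to identify significant differences between the two groups (controls and PF"). The summary sentence that follows again speaks of two groups.

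The last analysis is the ROC step: "we evaluated the diagnostic potential of significant FAs for IPF using Receiver Operating Characteristic (ROC) curves". That sentence names the target, IPF. It does not say who the ROC cases are, who the non-cases are, or which test makes an FA significant. No other sentence compares IPF with other fibrotic ILD. The documents do not say who the controls are, how many people are in any group, or what clinical use the markers would have.

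**The concern.** The conclusion sought is specific to one disease, and the only stated contrast is not. Controls versus pooled PF asks whether an FA differs between people with fibrotic lung disease and controls. An FA that changes to the same degree in every fibrotic lung disease would tend to pass that comparison. It would also do well in an ROC against controls, although it carries no information on whether a patient has IPF or another fibrotic ILD.

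Using one contrast throughout would not remove the problem. If both the selection of FAs and the ROC compared IPF with controls, the AUC would still not separate an IPF marker from a fibrosis marker. At stake is whether an AUC from this study can be described as diagnostic potential for IPF. The study enrols the patients in whom that could be examined, but the plan does not say that they will be used in this way.

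**Working it through.** The documents give no AUC, effect size, sample size or power, so there is no stated figure to reproduce. The effect sizes and group sizes below are assumptions.

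**Step 1. The possible readings of the ROC sentence.**

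| Cases | Non-cases | What a high AUC shows |
|---|---|---|
| All PF | Controls | Separation of fibrotic lung disease from controls |
| IPF | Controls | Separation of IPF from controls; silent on other fibrotic ILD |
| IPF | Other fibrotic ILD | Separation of IPF from other fibrosis |

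Only the third row supports a claim specific to IPF. The first matches the one contrast that the plan states.

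**Step 2. A marker of fibrosis in general.** Assume normal values with equal variance, and a shift of d SD from controls that is the same in IPF and in other fibrotic ILD. Then AUC = Phi(d / sqrt 2).

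| Shift shared by all fibrotic ILD | AUC against controls | AUC, IPF against other fibrotic ILD |
|---|---|---|
| 0.8 SD | Phi(0.566) = 0.714 | Phi(0) = 0.500 |
| 1.0 SD | Phi(0.707) = 0.760 | 0.500 |
| 1.5 SD | Phi(1.061) = 0.856 | 0.500 |

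The middle column holds whether the cases are IPF only or all PF, because the shift is shared. If IPF adds a further 0.2 SD, the AUC for IPF against other fibrotic ILD is Phi(0.2 / sqrt 2) = Phi(0.141) = 0.556.

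**Step 3. A marker specific to IPF under the pooled comparison.** If only IPF is shifted, and IPF makes up a share p of the PF group, the AUC for PF against controls is p × Phi(d / sqrt 2) + (1 − p) × 0.5. With d = 0.8:

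- p = 0.3: 0.3 × 0.714 + 0.7 × 0.5 = 0.564
- p = 0.5: 0.5 × 0.714 + 0.5 × 0.5 = 0.607
- p = 0.7: 0.7 × 0.714 + 0.3 × 0.5 = 0.650

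For IPF against other fibrotic ILD the same marker has AUC 0.714. Pooling therefore dilutes the markers that an IPF claim needs, and selection by the controls-versus-PF p-value could drop them.

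**Step 4. Precision of an ROC within the patients.** At AUC 0.5, SE = sqrt((m + n + 1) / (12mn)), with m IPF patients and n other-ILD patients.

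- Assumed 60 and 30: sqrt(91 / 21,600) = 0.065; 95% half-width 1.96 × 0.065 = 0.127.
- Assumed 40 and 20: sqrt(61 / 9,600) = 0.080; half-width 0.156.

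An observed AUC of 0.50 would have an upper limit of about 0.63 or 0.66, below all three control-based values in Step 2. Around an AUC of 0.556, the same half-widths give about 0.43 to 0.68 or 0.40 to 0.71, and both intervals include 0.50. The variance always exceeds 1 / (12n). With 20 other-ILD patients the half-width therefore stays above 1.96 × sqrt(1/240) = 0.127 however many IPF patients there are, and it is wider with fewer other-ILD patients.

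**The case against.** Three objections carry weight.

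First, a reader might infer that the other-ILD patients are never used as non-cases, and that a general fibrosis marker will therefore be reported as diagnostic for IPF. The documents do not go that far. The reference to controls and PF belongs to the tests of group differences, and the ROC sentence names no non-cases, so it does not exclude IPF versus other fibrotic ILD. One figure is not shown, and the heading Study Protocol Design has no text beneath it, so a group layout given there cannot be checked. The consequence is conditional on the ROC using controls.

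Second, IPF in the ROC sentence may be loose wording for PF, which is the label used for the study title, the population and the stated contrast. If so, a change of wording is enough and no new analysis is needed. That stands, and the fix allows for it. It would also be too strong to make IPF versus other fibrotic ILD the sole test of diagnostic potential, because the documents state no intended clinical use.

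Third, a reader might infer that the extra ROC is informative with the patients already enrolled. No group sizes are given, so this cannot be asserted. The ROC could help to exclude a large AUC, but it could not resolve a small difference at the sizes assumed above. Opening it to every FA also adds comparisons to a plan whose only stated rule is that a p-"value < 0.05 was considered statistically significant", with no adjustment described.

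These objections limit the claim but do not remove it. On each reading of the ROC sentence, the plan needs a change before the conclusion can be worded.

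**Conclusion.** The point holds in conditional form. The plan seeks a conclusion about IPF, states only a controls-versus-pooled-PF contrast, and leaves the ROC non-cases undefined. If the non-cases are controls, an AUC of 0.71 to 0.86 is compatible with no ability at all (0.50) to tell IPF from other fibrotic ILD. That range rests on normal, equal-variance values and an assumed shared shift of 0.8 to 1.5 SD, none of which comes from the documents. If the non-cases are other fibrotic ILD, the plan should say so, and selecting FAs by what appears to be the controls-versus-PF test is then the wrong filter. If IPF was meant as PF, the wording needs correcting. The plan should be changed on this point because it bears on the study's diagnostic conclusion.

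**What to change.** In the Statistical plan:

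1. Name the cases and non-cases of every ROC curve.
2. Report the AUC against controls as separation of disease from controls, and nothing more.
3. For any claim specific to IPF, add an ROC with IPF patients as cases and the enrolled other fibrotic ILD patients as non-cases, with a 95% CI. Do not make entry depend on the controls-versus-PF p-value. Label the analysis exploratory and state how many FAs were tested.
4. If that ROC is not run, or if IPF was meant as PF, limit the conclusion to PF versus controls.

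The cost is a few sentences and one further ROC per FA in patients already enrolled, with no new procedures. The IPF-specific AUC will probably be lower than the AUC against controls. Its interval may be wide, so the number of patients in each stratum should be reported beside it. Removing the p-value filter increases the number of FAs examined, which is why the exploratory label and the count are needed.

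### Fatty acids appear to reach the ROC step on an unadjusted p < 0.05, so the share of false diagnostic candidates is uncontrolled

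*Combined protocol and SAP*

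**What the plan says.** The section headed Statistical plan is one paragraph. Four of its statements matter here:

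- For continuous variables, "the Wilcoxon-Mann-Whitney test was used for continuous variables to identify significant differences between the two groups (controls and PF".
- The methods are said to cover "the clinical and biochemical differences between the two groups and the relationships among the fatty acids studied".
- As the last analysis, "we evaluated the diagnostic potential of significant FAs for IPF using Receiver Operating Characteristic (ROC) curves".
- The only significance rule is "A p -value < 0.05 was considered statistically significant".

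FAs are plural, but the readable text gives no number. It names no primary FA, familywise or false-discovery adjustment, testing order or validation set, and it does not call the screen exploratory.

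The opening section (Study Protocol and Statistical Plan) also admits patients with a "diagnosis of other fibrotic interstitial lung disease different from IPF". The PF group is therefore wider than IPF, the disease named for the ROC step.

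**The concern.** The Wilcoxon sentence does not name FAs, so the path from test to candidate has to be inferred. An FA can only be significant by some test. The only two-group test given for continuous variables is the Wilcoxon-Mann-Whitney, and the only threshold is 0.05. On that reading each FA has its own 5% chance of passing when it does not differ between the groups, and nothing limits how many of the FAs put forward arrived that way.

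The ROC step offers little protection. On the same participants and contrast, the AUC is the Mann-Whitney statistic rescaled, so an FA that passed by chance also shows an AUC away from 0.5. Noise could then be described as having diagnostic potential. The concern covers only the FA tests that feed the ROC step, not the baseline comparisons or the correlations.

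**Working it through.** **Inputs.** The document gives the 0.05 threshold; I take it as two-sided, which is not stated. All other inputs are assumptions: number of FAs k, number that truly differ, effect size in SD, n per group, and correlation among FAs. The plan states no error rate or power, so there is no figure of its own to reproduce.

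**1. Expected false share among FAs with raw p < 0.05, independent FAs.** Let V ~ Bin(m0, 0.05) be the null FAs that pass and S ~ Bin(m1, π) the real ones that pass, with π the power of one test. The false share is the mean of V/(V+S), counted as 0 when nothing passes. Simulated Mann-Whitney power is π = 0.970 at 0.8 SD with n = 50 per group, and 0.455 at 0.5 SD with n = 30.

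| FAs (real) | Effect, n per group | m0 × 0.05 | m1 × π | False share, formula | Raw, simulated | Benjamini-Hochberg, simulated |
|---|---|---|---|---|---|---|
| 10 (4) | 0.8 SD, 50 | 0.30 | 3.88 | 5.9% | 5.9% | 3.0% |
| 20 (4) | 0.8 SD, 50 | 0.80 | 3.88 | 14.6% | 14.2% | 3.6% |
| 20 (1) | 0.8 SD, 50 | 0.95 | 0.97 | 36.6% | 36.7% | 4.3% |
| 50 (1) | 0.5 SD, 30 | 2.45 | 0.455 | 78.8% | 78% | – |

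The share depends on the fraction of FAs that truly differ as well as on panel size.

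**2. Chance of at least one false candidate if no FA differs.** With independent FAs this is 1 − 0.95^k:

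- k = 2: 1 − 0.9025 = 9.75%
- k = 5: 1 − 0.7738 = 22.6%
- k = 10: 1 − 0.5987 = 40.1%
- k = 20: 1 − 0.3585 = 64.2%

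For the same four k, equal correlation of 0.5 gives 9/18/29/42%, and 0.8 gives 8/13/17/22%. Perfect dependence returns 5%.

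**3. What Benjamini-Hochberg does to that chance.** It controls the false share. Once some FAs truly differ, it does not hold the any-false-candidate chance at 5%. Simulated values after adjustment (independent, 0.8 SD, n = 50) are 13% (10 FAs, 4 real), 16% (20, 4 real) and 22% (20, 8 real).

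**4. AUC of a null FA that passes.** Since AUC = U/(n1 × n2), p < 0.05 needs at least

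0.5 + [1.96 × √(n1·n2·(n1+n2+1)/12) + 0.5]/(n1·n2).

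- n = 50 per group: √(2500 × 101/12) = 145.06; (284.31 + 0.5)/2500 = 0.114; AUC at least 0.614.
- n = 30 per group: √(900 × 61/12) = 67.64; (132.57 + 0.5)/900 = 0.148; AUC at least 0.648.

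If the screen uses all PF but the ROC uses IPF only, the floor is no longer strict. With IPF at 50-80% of the PF group, the simulated mean AUC of a selected null FA is still about 0.635 (n = 50) or 0.676 (n = 30).

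**The case against.** **The link is inferred, and figures may be missing.** The Wilcoxon sentence does not mention FAs, and the document has a figure that is not shown, which could hold the panel or sample size. That is fair, and I do not count those absences as errors. It does not supply a multiplicity rule in a paragraph that sets out the tests and the threshold.

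**The study is exploratory in nature.** It is single-center and cross-sectional and speaks only of diagnostic potential. Leaving the screen unadjusted would be defensible if it were labelled exploratory, with the number tested and all raw p-values reported. This stands, and the fix offers it as an alternative. The present text carries no such label.

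**Adjustment costs power.** This also stands; the loss is large in a small study or with weak effects.

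**Three stronger readings are tempting, and none is supported.**

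- A reader might infer that the plan fails because the chance of any false candidate exceeds 5%. The document sets no familywise standard, and the proposed adjustment would not meet one either (step 3). The false share is the better measure.
- A reader might infer that the ROC cannot reveal a false FA. A larger AUC still carries some information. At n = 50 a selected null FA averages 0.636 and 1% reach 0.70, whereas a selected 0.8 SD FA averages 0.718 and 64% reach 0.70. At n = 30, 14% of selected nulls reach 0.70, so the separation is poorer.
- A reader might take the highest tabulated share as a worst case. It reflects the assumptions chosen; no upper bound is claimed.

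**Conclusion.** The point holds, with moderate confidence, and should be fixed. On the natural reading, an unadjusted p < 0.05 is the only stated gate to diagnostic candidacy, and the share of false candidates is uncontrolled. Under the assumed conditions that share runs from about 6%, close to harmless, with few FAs of which many are real, to well over a third when few are real. The document does not let anyone say where this study lies. A same-sample ROC on the same contrast is not independent confirmation.

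The conclusion rests on the inferred link between the Wilcoxon tests and the significant FAs, on tests of true size near 0.05, and on more than one FA being tested. It does not show that any particular FA is a false finding.

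**What to change.** State the number of FAs tested and whether the ROC contrast is IPF versus controls or all PF versus controls. Then add to the Statistical plan:

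> The tests of all FAs on the same contrast as the ROC form one family; raw p and Benjamini-Hochberg q are reported for every FA. ROC curves are drawn for FAs with raw p < 0.05; those with q >= 0.05 are labelled exploratory. Statements of diagnostic potential are reserved for FAs with q < 0.05 on that contrast. All AUCs are apparent and need independent validation.

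The family must follow the ROC contrast. A q-value from controls versus all PF would not protect a statement about IPF, because an FA that differs only in the other fibrotic diseases could pass.

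If the sponsor prefers not to adjust, the alternative is to label the whole FA screen and its ROC results exploratory, report the number tested and all raw p-values, and make no diagnostic statement without independent validation.

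**Cost.** A few sentences and one line of code; no ROC curve is lost. Fewer real FAs would support a diagnostic statement. With 20 independent FAs, 4 real, per-FA sensitivity falls from 97% to about 88% (0.8 SD, n = 50 per group), from 84% to 57% (0.8 SD, n = 30) and from 46% to about 13% (0.5 SD, n = 30). This is why FAs that pass only on raw p keep their curves, marked exploratory.
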